#### Participant Recruitment

#### **Eligibility Criteria**

The in-/exclusion criteria are deliberately broad to allow the inclusion of a large and varied population representative of "real-life" respiratory patients. We are targeting asthma and COPD as they are the most common problems, with validated symptom questionnaires.

#### Inclusion criteria

Either COPD or asthma, as defined by their referring/usual care clinician in the medical record. The same inclusion criteria apply across all 3 parts of the study. Participants in this study need to be over the age of 16 and able to give informed consent.

#### Exclusion criteria

Patients unwilling or unable to participate in the study; again, this applies across all 3 parts of the study.

#### **Recruitment target**

#### Size of recruitment target

The target sample size is based on experiences with similar projects, with 30 likely to be sufficient to reach data saturation, and 100 likely to give sufficient pilot data to design onward studies of interventions (parts 1 and 2 respectively). The number of patients who can have home monitoring is a pragmatic choice made from availability of monitors and knowledge of sample size in other interventional studies; without data on the extent to which indoor AQ relates to symptoms in COPD and asthma it is impossible to conduct a robust power calculation. Notably the data from part 3 of the study would be used to aid power calculations for onward interventional studies.

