#### Part 3: Quantifying indoor AQ and respiratory symptoms

This part of the study will recruit approximately 60 patients, aiming for an equal distribution of people with asthma and people with COPD. Any severity stage will be allowed. In a study of an air purifier in asthmatic children a 4% difference in PEFR variability was seen [5]; the study had power 80% and  $\alpha$ =0.05, and it was possible to detect this with 30 patients in each arm of a study. Consequently, we feel that 30 is a reasonable target per condition in an exploratory study of this nature in adults.

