#### **Analysis**

Simple descriptive statistics will be used to delineate characteristics of the cohort, and the correlation between each pollutant measured by the indoor monitor and day to day symptoms, as determined by the total score on Bronkotest® or ACT. In addition, daily puffs of inhaled short acting treatment (salbutamol) and (asthma only) PEFR will also be examined for relationship to indoor AQ, using a similar correlation analysis. Other factors relating to indoor AQ within collected demographic and medical history data will also be reported using simple comparative statistics.

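### Part 3 is meant to inform the power of later intervention studies, but correlation is the only pollutant-outcome measure its analysis names; a slope per unit of pollutant and the SDs should be named too

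*Protocol*

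**What the plan says.** Two sections of the protocol matter here.

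- **Size of recruitment target.** After explaining that no robust power calculation is possible for Part 3, the section gives a forward use: the Part 3 data "would be used to aid power calculations for onward interventional studies".
- **Part 3, Analysis.** The main relationship to be described is "the correlation between each pollutant measured by the indoor monitor and day to day symptoms", with symptoms taken "as determined by the total score on Bronkotest® or ACT". Daily salbutamol puffs and, in asthma only, PEFR are to be related to indoor air quality "using a similar correlation analysis". Two other outputs are planned: "Simple descriptive statistics will be used to delineate characteristics of the cohort", and other factors related to indoor air quality "will also be reported using simple comparative statistics".

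The Analysis section names no regression slope. It also names no SD or variance component for the daily outcomes or for the pollutants.

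The target is about 60 patients, half with each condition, with daily diary entries for at least two weeks. The Background section gives a concrete idea of a later intervention: air purifiers, with a PM2.5 reduction of up to 57%.

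**The concern.** Someone planning a purifier trial starts from a reduction in PM2.5 and needs the change in symptoms that it might produce, set against the variability of those symptoms. A correlation answers a different question: how tightly two variables move together in this particular sample. The same true effect per unit gives a small r where homes are alike in pollution and a larger r where they differ.

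The named measure therefore does not match the stated later use. If the Part 3 report gave r alone, a reader could not recover the expected effect without going back to the raw data. Anyone who read r across to a population with a different pollution spread would get the wrong trial size.

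**Working it through.** **The plan's own figure.** The only sample-size figure near Part 3 is the cited children's study: a 4% difference in PEFR variability, 80% power, α = 0.05, 30 per arm. No SD is given, so 30 cannot be reproduced. Solving backwards from n per arm = 2[(z_α + z_β)·SD/δ]² gives SD = 4 / [(1.960 + 0.842)·√(2/30)] ≈ 5.53 points if the test is two-sided (6.23 if one-sided). The figure can be neither confirmed nor refuted, and nothing below depends on it.

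**Inputs.** From the protocol: the 57% reduction (Background) and 30 patients per condition (Part 3). Assumed for illustration: r = 0.3; pollutant SD (SDx) of 5, 10 and 20 units; outcome SD (SDy) of 2, 4 and 8 points; a 5-unit pollutant reduction; pollutant coefficient of variation (CV) of 0.5, 1.0 and 1.5; 80% power, two-sided 5%.

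**Step 1: r does not fix the slope.** Since r = b·SDx/SDy, the slope is b = r·SDy/SDx. With r = 0.3:

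- lowest: 0.3 × 2/20 = 0.03 points per unit
- highest: 0.3 × 8/5 = 0.48 points per unit

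One r is compatible with a 16-fold range of slopes (0.48/0.03).

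**Step 2: what r implies for a two-arm trial.** For a pollutant reduction ΔX, the standardised effect is d = b·ΔX/SDy = r·ΔX/SDx. The outcome SD cancels and the pollutant SD does not. With n per arm = 2[(1.960 + 0.842)/d]² and ΔX = 5:

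| SDx | d | n per arm |
|---|---|---|
| 5 | 0.300 | 175 |
| 10 | 0.150 | 698 |
| 20 | 0.075 | 2791 |

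**Step 3: the protocol's 57% reduction.** If ΔX is 57% of the mean and SDx is CV times the mean, then d = r × 0.57/CV. With r = 0.3:

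| CV of pollutant | d | n per arm |
|---|---|---|
| 0.5 | 0.342 | 135 |
| 1.0 | 0.171 | 537 |
| 1.5 | 0.114 | 1208 |

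That is about a nine-fold range (1208/135) from the same r.

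**Step 4: why the outcome variance components still help.** The cancellation in Step 2 holds only if the later trial's outcome has the same SD as the one behind r. A trial might well average daily scores. With intraclass correlation ICC and independent within-person errors, the variance of a 14-day mean relative to a single day is ICC + (1 − ICC)/14. For assumed ICCs of 0.3, 0.6 and 0.8 this is 0.35, 0.63 and 0.81. For a fixed raw effect n is proportional to this variance, so it differs by a factor of about 2.3 (0.81/0.35).

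**Step 5: precision at 30 per condition.** With one pair of values per person, Fisher's z for r = 0.3 is 0.3095, with half-width 1.96/√27 = 0.377. Back-transformed, the 95% CI is about −0.07 to 0.60. Repeated days may narrow this; by how much cannot be worked out from the protocol.

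**The case against.** The strongest reply has four parts.

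- **The protocol says the data, not the coefficients, will aid later power calculations.** This stands. Daily scores, PEFR and particulate readings are all collected, and slopes and SDs can be computed from them later. A reader might infer that the study would end without the quantities it needs; the protocol does not support that.
- **Correlations are not the only output.** This also stands. Descriptive and comparative statistics are planned, and a pollutant SD is an ordinary descriptive statistic. What remains is narrower: correlation is the only measure named for the pollutant-outcome relationship.
- **Nobody proposes to use r as an effect size, and the outcome SD is not always needed.** Both are right. No section plans to size a trial from r, so mis-sizing is a risk if r is all that is reported, not an error in the plan. For a simple two-arm comparison, r and the pollutant SD are enough (Step 2). The outcome SDs matter for effects in score units and for designs that use repeated days.
- **Such output lists belong in a statistical analysis plan, and power planning is not a stated objective.** This stands in part. An analysis plan may exist that is not shown, the study is exploratory ("we feel that 30 is a reasonable target per condition in an exploratory study of this nature in adults"), and the listed objectives do not mention power. But the protocol does not leave the measure open. It names correlation and, separately, a use that correlation alone does not serve.

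**Conclusion.** The point holds as a minor improvement in fit to purpose. Correlation is the only pollutant-outcome measure named for symptom score, salbutamol puffs and PEFR, and on its own it does not give the symptom change expected for a given pollutant reduction. At r = 0.3, the implied trial size runs from 175 to 2791 per arm for a 5-unit reduction, or from 135 to 1208 for a 57% reduction, depending only on the pollutant spread.

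These ranges rest on assumed values of r, SD and CV, since the protocol gives none, and on reading an observational association as if it were the effect of an intervention. They show how much r leaves undetermined; they do not forecast a trial size. The protocol contains no wrong number on this point and no contradiction that would stop the study serving its purpose.

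**What to change.** **In Part 3, Analysis**, add that for each condition and outcome the report will give, alongside any correlation:

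- the regression slope per 10 µg/m3 PM2.5, and per unit of each other pollutant where the issued device measures it (Appendix 4 lists PM2.5 alone for the third-choice device), with a 95% CI from a model that accounts for repeated days within a person;
- the mean, between-person SD and within-person SD of the daily outcomes (symptom score, salbutamol puffs and, in asthma, PEFR) and of daily PM2.5.

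**In Size of recruitment target**, state that later power calculations will draw on these estimates and not on r, and that an observational slope is not an intervention effect.

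The lower confidence limit of the slope should not be written in as a cautious planning value. With 30 per condition it can lie at or below zero, as in Step 5, and it then yields no usable sample size.

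The cost is a few sentences of protocol text and a modest amount of extra analysis on data already being collected. No new visits, measurements or participants are needed.

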#### Participant identification and recruitment technique

Potential participants will be identified from existing databases of subjects with known respiratory conditions who have previously indicated that they are willing to take part in research. Participants will be identified by practitioners who have access to these databases from their own previous research or as part of their role as a practitioner of respiratory medicine. These practitioners will approach potential participants and discuss the study with them.

Both follow-up and new patients referred to specialist NHS respiratory clinics at the research site will also be approached about the study by members of the research team.

The study will also be advertised via respiratory patient advocacy and support groups.

If patients are interested in the research, the team will then contact them to consent to the study and conduct study related procedures (for example provide the PIS and other documents).

In addition, we will advertise publicly for participants using a poster which can be put up in participating NHS sites and will also be put onto the CleanAir4V study website and social media.

#### Consent

Informed consent will be taken by an appropriately trained individual in accordance with GCP who has been delegated to do so by the CI. Consent will be taken and documented fully prior to any study related procedures being performed, and will be separate for each part of the study.

#### Safety reporting

This is an observational study therefore adverse and serious adverse events are not expected, however procedures will be place in case of an event. Adverse events (AE), defined as any untoward medical occurrence in a study participant, which does not necessarily have a causal relationship with the study, can be any unfavourable and unintended sign (including abnormal laboratory finding), symptom, or disease. All adverse events reported spontaneously by the participant or observed by the Chief Investigator or their staff will be recorded.

A serious adverse event (SAE) is any untoward medical occurrence or effect that:

- results in death;
- is life threatening (at the time of the event);
- requires hospitalisation or prolongation of existing in patients' hospitalisation;
- results in persistent or significant disability or incapacity;
- is a congenital anomaly or birth defect;
- is a new event of the trial likely to affect the safety of the participants, such as an unexpected outcome of an adverse reaction, lack of efficacy of an IMP used for the treatment of a life-threatening disease, major safety finding from a newly completed animal study, etc.

Any Serious Adverse Event, with a possible relation to the study will be reported by the Chief Investigator to the National Co-ordinating Centre within 24 hours of being made aware of the event, who will then forward on to

the Research Ethics Committee and University of Birmingham Research Governance team within 15 days. Any SAE not, or unlikely to be related to the study, will be reported to the Funder of the Network (NERC) and the National Institute for Health Research (NIHR) by the Chief Investigator within 24 hours.

All adverse events will be followed until they have abated, or until a stable situation has been reached. Depending on the event, follow up may require additional tests or medical procedures as indicated, and/or referral to the general physician or a medical specialist.

#### **Ethical and regulatory considerations**

This study does not contain any major ethical issues since it is observational in nature and does not ask intrusive questions. It will be made clear to participants that benefit is likely to be others and not to them personally, with the possible exception of part 3, which may benefit patients by giving them a greater understanding of their own personal indoor AQ, and its impact on their respiratory symptoms. All routine ethical procedures for research in the NHS will be followed, specifically: *REC and HRA*.

Before the start of the study, approval will be sought from a REC and the HRA for the trial protocol, informed consent forms and other relevant documents e.g. advertisements and GP information letters. Substantial amendments that require review by REC will not be implemented until the REC grants a favourable opinion for the study. All correspondence with the REC will be retained in the Trial Master File/Investigator Site File. An annual progress report (APR) will be submitted to the REC within 30 days of the anniversary date on which the favourable opinion was given, and annually until the trial is declared ended. The CI (or delegate) will produce the annual reports as required and notify the REC of the end of the study. If the study is ended prematurely, the CI will notify the REC, including the reasons for the premature termination. The CI (or delegate) will submit a final report with the results, including any publications/abstracts, to the REC.

#### NHS permission

Before enrolling patients into the study, the CI or designee will apply for NHS permission from the site's Research & Development (R&D) department.

#### Registration of Trial

This trial will be registered to the ISRCTN, which is a primary clinical trial registry recognised by WHO and ICMJE that accepts all clinical research studies (whether proposed, ongoing or completed).

#### **Amendments**

If amendments are made these will be approved by the sponsor prior to submission to the REC and HRA. For any amendment that will potentially affect a site's NHS permission, the CI or designee will confirm with that site's R&D department that NHS permission is ongoing (note that both substantial amendments, and amendments considered to be non-substantial for the purposes of REC and/or HRA may still need to be notified to NHS R&D).

#### Protocol compliance

The procedures and assessments detailed in the study protocol should be followed at all times, however, accidental protocol deviations can happen and they must be adequately documented on the relevant forms and reported to the sponsor immediately. Deviations from the protocol which are found to frequently recur are not acceptable, will require immediate action and could potentially be classified as a serious breach.

A "serious breach" is a breach which is likely to effect to a significant degree -

- a) the safety or physical or mental integrity of the subjects of the trial; or
- b) the scientific value of the trial

The sponsor will be notified immediately of any case where the above definition applies during the trial study.

#### Data protection and patient confidentiality

All investigators and study site staff will comply with the requirements of the Data Protection Act 2018 and GDPR 2018 with regards to the collection, storage, processing and disclosure of personal information and will uphold the Act's core principles. All data will be de-identified before being stored electronically on secure University servers. All source documents will be stored according to University of Birmingham SOPs and the Trial Master File (TMF) and Investigator Site File (ISF) will be stored in a secure office location by the study co-ordinator.

#### Indemnity

This study is covered by the standard University of Birmingham clinical trials insurance (see https://intranet.birmingham.ac.uk/finance/insurance/Clinical-Trials.aspx). In addition, any process occurring at an NHS site will have additional NHS indemnity.

#### End of study and archiving

After the final report has been sent, study documents will be archived for 10 years from the end of the study, as per the University of Birmingham guidelines

#### Access to the final study dataset

All those involved in developing the protocol will have access to the final study dataset. All participants will also be given the option to receive a lay summary of the results of the study when they are published. This information will be collected as part of the consent form at the beginning of the study.

#### Dissemination policy

The sponsor owns the data arising from the study and on completion of the study, the data will be analysed and tabulated and a Final Study Report prepared. This will be available via academic publications arising from the work and from the lead researcher for the parent project ([name]) or the sponsor on request. It is anticipated that all protocol authors will be authors on publications arising, assuming they meet the guidance for authorship in each individual part of the work.

#### **Appendices**

#### **Appendix 1- Required documentation**

- CVs of research team members
- Patient information sheet (parts 1, 2 and 3)
- Consent form
- GP information letter
- Bronkotest® questionnaire
- ACT questionnaire
- Representative screenshots from the electronic form of the questionnaire

#### Appendix 2 – Schedule of Procedures

Study part	Visit 1	Daily participation	Visit 2
1	Consent, interview	-	-
2	Consent, questionnaire	-	-
3	Consent, demographics, medical history, issue of AQ monitor	Daily symptoms	Collection of AQ monitor

#### Appendix 3 – Amendment History

Amendment No.	Protocol Version No.	Date Issued	Author(s) of Changes	Details of Changes
1	6.1	14.04.2022	[name]	Edits to Part 4 – Study Design and methods of data collection and data analysis:
				
 
Minor grammatical changes
 
Addition of timescales for questionnaires
 
Addition of information about AQ devices
 

2	6.1	14.04.2022	[name]	Edits to Participant Recruitment: - Removal of children from the eligibility criteria.
3	6.1	14.04.2022	[name]	Edits to Registration of Trial: -Trial will be registered with the ISRCTN
4	6.1	14.04.2022	[name]	Edits to Appendix: -Addition of Appendix 4 (Information about Air Quality Sensors)
5	6.2	28.04.2022	[name]	Grammar check to document and images added to Appendix 4.

List details of all protocol amendments here whenever a new version of the protocol is produced.

Protocol amendments must be submitted to the Sponsor for approval prior to submission to the REC.

Appendix 4 – Information about Air Quality Devices, in preferred order.

Name of Air	Basic Information	Preference	Additional	Image
Quality Device		of Use	Information	
Plume Labs Flow	Pollutants Measured: PM1,	First	- Not Weatherproof.	
2	PM2.5, PM10, NO2, VOCs		- Data is transferred	
Plume Labs - Flow	Size: 125mm x 40mm x 35mm		via Bluetooth (no	
2 (aqmd.gov)	Weight: 70g		data stored	
z (aqmu.gov)	Power Supply: USB Cable		internally.	
	Sampling Mechanism: Fan,		- 24-hour battery	Tracks.
	Laser Particle Counter		life.	2xt#
	(Particle Matter), Heated			
	Metal Oxide Sensor (Gases)			
	Price: £151.50 (14.04.2022)			
AirBeam	Pollutants Measured: PM1,	Second	- Temperature and	
	PM2.5, PM10		Relative Humidity	
AirBeam2	Size: 132mm x 98mm x 28mm		can also be	
Technical	Weight: 142g		measured.	
Specifications,	Power Supply: USB C Cable		- Data is transferred	
Operation &	Sampling Mechanism:		via Wi-Fi (no data	
Performance	Sensing Chamber		stored internally).	
(habitatmap.org)	Price: £189.50 (14.04.2022)		- 10-hour battery	
			life.	
December Aire DA I	Dellestante Maranente DMA2 F	The inval	Durana	
Purple Air PA-I-	Pollutants Measured: PM2.5	Third	- Pressure,	
Indoor	Size: 108mm x 67mm x 57mm		Temperature and	
PurpleAir PA-I-	Weight: N/A		Relative Humidity	
Indoor Air Quality	Power Supply: USB A Cable		can also be	
Sensor - PM2.5	Sampling Mechanism: Laser		measured.	
Detector	Particle Counter		- Indoor Use Only.	
= ======	Price: £151.50 (14.04.2022)		- Data is transferred	
			via wi-fi (no data is	
			stored (internally).	
				makes to the book of the control of
